5.7 Criteria to Resume Treatment

Management of adverse events is summarized in section 6 and may include holding of nivolumab and ipilimumab, and/or the use of steroids for the management of immune related AEs.

If drug administration is held until the next scheduled time point, please continue to count weeks/doses. If patients must be delayed due to toxicity, all assessments can be obtained with the modified treatment dose schedule as noted in this section.

Some patients may continue to benefit from treatment, maintaining or improving responses after progression including those treated with steroids.

Restarting nivolumab may be considered in patients who experience grade 2 events and some grade 3 events (skin rash and thyroiditis). Because of this, stopping treatment and starting steroids earlier, as per section 6, to obtain resolution with the possibility for restarting rather than waiting for higher grade events is encouraged.

For non-autoimmune or non-inflammatory events patients may resume treatment with study drug when the drug-related AE(s) resolve to Grade ≤ 1 or baseline value, with the following exceptions:

- Evaluation to exclude any additional immune mediated events endocrine, GI, and liver / pancreas function as clinically indicated must be made prior to restarting.
- Non-drug-related toxicity including hepatic, pulmonary toxicity, diarrhea, or colitis, must have resolved to baseline before treatment is resumed.

If the criteria to resume treatment are met, the patient should restart treatment no sooner than the next scheduled time point per protocol. However, if the treatment is delayed past the next scheduled time point per protocol the treatment should resume at the earliest convenient point that is within the six week delay period.

For protocols using combination nivolumab/Ipilimumab for the initial induction period patients with grade 2 or 3 events requiring discontinuation of treatment with the combination, the PI may consider continuing treatment with single agent nivolumab at the same dose when the event resolves to baseline. However, patients with renal, CNS, or pulmonary toxicity must be removed from study.

For patients treated with corticosteroids:

For patients treated with high dose steroids with nivolumab/Ipilimumab, toxicity must resolve to baseline within 8 weeks of treatment.

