Patients should be off steroids for at least 2 weeks with no recurrence or new events. New immune related events or exacerbation of existing events during steroid treatment or taper suggest the presence of ongoing immune activation and should require permanent discontinuation of nivolumab.

Grade 2 events must resolve to grade ≤ 1 before considering retreatment.

All patients treated with steroids for grade ≥ 2 events should have nivolumab held until resolution to grade ≤ 1 for at least 2 weeks following complete removal from steroid treatment except for maintenance replacement doses for adrenal insufficiency (preferably no greater than 10mg prednisone equivalent daily).

All patients treated with steroids for grade ≥ 3 events should have nivolumab discontinued. Patients with grade 3 thyroiditis and skin rash may continue therapy as for grade 2 events with resolution and stable replacement treatment.

Patients with hepatitis, pancreatitis, pneumonitis, and colitis are at risk for exacerbation with retreatment if there is residual inflammation and should resolve to Grade 0 or baseline before retreatment. Baseline can mean the initial grade *i.e.* grade <1 where permitted on study.

Patients with thyroiditis or hypopituitarism who are stable as above may be restarted with replacement hormones including thyroid hormone and physiologic doses only of corticosteroids. Please note that grading and for hypophysitis with symptoms of headache, visual or neurologic changes or radiologic evidence of pituitary enlargement and other CNS events such as aseptic meningitis or encephalitis should be considered grade 3 events.

New immune related events or exacerbation of existing events during steroid treatment or taper suggest the presence of ongoing immune activation and should require permanent discontinuation of nivolumab.

A patient who is treated with steroids, evaluated, and found to not have an autoimmune or inflammatory event requiring steroid treatment, may be restarted if asymptomatic off steroids for 2 weeks and other restarting criteria are met.

Prior to starting corticosteroids or hormone replacement for any reason, appropriate endocrine

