| ≤ Grade 1 | Evaluate and continue treatment at same level at investigator discretion. |
| Grade 2 | Hold until Grade ≤1 or baseline following treatment algorithm; evaluate and resume at investigator discretion if additional therapy is not required. |
| Grade 3 | Hold until Grade ≤1 or baseline following treatment algorithm; evaluate and resume at investigator discretion. |
| Grade 4 | Off protocol therapy |
| See GI AE Algorithm for management of symptomatic colitis. Patients with grade 2 symptoms but normal colonoscopy and biopsies may be retreated after resolution. Please evaluate pituitary function prior to starting steroids if possible without compromising acute care. Evaluation for all patients for additional causes includes C. diff , acute and self-limited infectious and foodborne illness, ischemic bowel, diverticulitis, and IBD. | |
| Recommended management: see GI AE management Algorithm | |

| Pancreatitis Amylase/Lipase | Management/Next Dose for Nivolumab and combination Nivolumab/ipilimumab |
|--|---|
| ≤ Grade 1 | Continue treatment at same level at investigator discretion. |
| Grade 2 | Continue treatment at same level at investigator discretion if asymptomatic. |
| Grade 3 | Hold until Grade ≤2 . Resume at same dose level if asymptomatic. Patients who develop symptomatic pancreatitis or DM should be taken off treatment. |
| Grade 4 | Hold until Grade ≤2 . Resume at same dose level if asymptomatic. Patients who develop symptomatic pancreatitis or DM should be taken off treatment. |
| Patients may develop symptomatic and radiologic evidence of pancreatitis as well as DM and DKA. Lipase elevation may occur during the period of steroid withdrawal and with other immune mediated events or associated with colitis, hepatitis, and patients who have asymptomatic lipase elevation typically have self-limited course and may be retreated. For treatment management of symptomatic pancreatitis please follow the Hepatic Adverse Event Management Algorithm. | |

| Pneumonitis | Management/Next Dose for Nivolumab and combination Nivolumab/ipilimumab |
|--|---|
| ≤ Grade 1 | Hold dose pending evaluation and resolution to baseline including baseline pO ₂ . Resume no change in dose after pulmonary and/or ID consultation excludes agent associated lymphocytic pneumonitis. |

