| Grade 2 | Hold dose pending evaluation. Resume no change in dose after pulmonary and/or ID consultation excludes nivolumab/ipilimumab associated lymphocytic pneumonitis As the cause of the pneumonitis. Off study if steroids are required. |
| Grade 3 | Hold dose pending evaluation. Resume no change in dose after pulmonary and/or ID consultation excludes nivolumab/ipilimumab associated lymphocytic pneumonitis as the cause of the pneumonitis. Off study if steroids are required. |
| Grade 4 | Off protocol therapy |
| Distinguishing inflammatory pneumonitis is often a diagnosis of exclusion for patients who do not respond to antibiotics and have no causal organism identified including influenza. Most patients with respiratory failure or hypoxia will be treated with steroids. Bronchoscopy may be required and analysis of lavage fluid for lymphocytic predominance may be helpful. Patients with new lung nodules should be evaluated for sarcoid like granuloma. Please consider recommending seasonal influenza killed vaccine for all patients. | |
| Recommended management: See Pulmonary Adverse Event Management Algorithm | |

| Other GI N-V | Management/Next Dose for Nivolumab and combination Nivolumab/ipilimumab |
|---|---|
| ≤ Grade 1 | No change in dose. |
| Grade 2 | Hold pending evaluation for gastritis duodenitis and other immune adverse events or other causes. Resume at investigator discretion. |
| Grade 3 | Hold pending evaluation until ≤ Grade 2. Resume at same dose level. If symptoms do not resolve within 7 days with symptomatic treatment patients should go off protocol therapy |
| Grade 4 | Off protocol therapy |
| Patients with grade 2 or 3 N-V should be evaluated for upper GI inflammation and other immune related events. | |

| Fatigue | Management/Next Dose for Nivolumab and combination Nivolumab/ipilimumab |
|---|--|
| ≤ Grade 1 | No change in dose. |
| Grade 2 | No change in dose |
| Grade 3 | Hold until ≤ Grade 2. Resume at same dose level at investigator discretion. |
| Grade 4 | Off protocol therapy |
| Fatigue is the most common adverse event associated with immune checkpoint therapy. Grade 2 or greater fatigue should be evaluated for associated or underlying organ involvement including pituitary, thyroid, and hepatic, or muscle (CPK) inflammation | |

| Cardiac * | Management/Next Dose for BMS-936558 (Nivolumab) + Ipilimumab Cardiac Toxicities |
|-------------------------------------|---|

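### For Grade 2 pneumonitis treated with steroids, 5.7 leaves retreatment open while the Section 6 table takes the patient off study, and nothing says which governs

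*Combined protocol and SAP*

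**What the plan says.** Three parts of 5.7 (Criteria to Resume Treatment) and two parts of Section 6 (Dosing Delays/Dose Modifications) bear on the point.

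- **5.7, opening.** Adverse event management is said to be summarised in Section 6. "Restarting nivolumab may be considered in patients who experience grade 2 events and some grade 3 events (skin rash and thyroiditis") is the general statement on restarting. Early interruption and early steroids are encouraged so that restarting remains possible.
- **5.7, combination induction.** After a Grade 2 or 3 event that ends the combination, single-agent nivolumab may be considered once the event is back to baseline. The paragraph then adds: "However, patients with renal, CNS, or pulmonary toxicity must be removed from study".
- **5.7, under the line "For patients treated with corticosteroids".** After steroids for a Grade 2 or higher event, nivolumab is to be "held until resolution to grade ≤ 1 for at least 2 weeks following complete removal from steroid treatment". After steroids for Grade 3 or higher it is discontinued, apart from thyroiditis and skin rash. Pneumonitis is then named among four events: "Patients with hepatitis, pancreatitis, pneumonitis, and colitis are at risk for exacerbation with retreatment if there is residual inflammation", and they "should resolve to Grade 0 or baseline before retreatment".
- **Section 6, pneumonitis table.** At Grades 2 and 3, dosing may resume only after consultation has excluded drug-associated lymphocytic pneumonitis. Both rows end: "Off study if steroids are required".
- **Section 6, closing text.** Patients who need high-dose steroids for autoimmune or inflammatory events are sent to 5.7. The exceptions are short tapering courses for infusion reaction, skin rash or endocrine events. Pneumonitis is not among them.

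**The concern.** A patient with Grade 2 pneumonitis who receives steroids, recovers fully and stays off steroids for 2 weeks can be handled in two ways, each with textual support. A site working from 5.7 may restart nivolumab. A site working from the Section 6 table takes the patient off study. Because 5.7 encourages early steroids in order to keep restarting possible, a site can follow that advice and trigger the clause in Section 6 that ends participation.

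The stake is re-exposure to study drug after an immune lung event. The toxicology background (2.2.1.2.3) reports pulmonary toxicity resulting in 3 deaths. Those were fatal events rather than resolved Grade 2 cases, so they show why lung toxicity deserves one clear rule; they do not measure the risk of retreatment. Different handling across sites would also make treatment exposure and reasons for discontinuation harder to interpret.

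**Working it through.** The plan states no figure on this point, so the check sets the passages side by side.

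**Step 1. By grade, for pneumonitis treated with steroids**

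| Grade | 5.7, corticosteroid paragraphs | 5.4 (Duration of Therapy) | Section 6 pneumonitis table | Result |
|---|---|---|---|---|
| 1 | Resolution to Grade 0 or baseline before retreatment | No stopping rule by grade | Hold to baseline; resume once drug-associated pneumonitis is excluded; no steroid clause | No direct conflict |
| 2 | Hold; retreatment open at Grade 0 or baseline and at least 2 weeks off steroids | No stopping rule by grade | Off study once steroids are required | **Conflict** |
| 3 | Nivolumab discontinued | Drug-related pneumonitis requires discontinuation | Off study once steroids are required | All stop drug |
| 4 | Nivolumab discontinued | Stop | Off protocol therapy | All stop drug |

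The conflict is therefore at Grade 2 only.

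**Step 2. By treatment phase in Cohort B**

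- *Combination induction (cycles 1 to 4).* The removal sentence for pulmonary toxicity in 5.7 agrees with the table for a steroid-treated case. It does not fit the corticosteroid paragraphs of the same section, which list pneumonitis among events that may be followed by retreatment. Here 5.7 is inconsistent with itself.
- *Nivolumab monotherapy (cycle 5 onwards).* The removal sentence belongs to a paragraph about combination induction and does not clearly reach this phase. The corticosteroid paragraphs of 5.7 and the Grade 2 row of Section 6 then stand directly against each other.

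The planned maximum durations are 4 cycles × 3 weeks = 12 weeks of induction and 46 doses × 2 weeks = 92 weeks of monotherapy. These are limits set by the schedule. They do not say how much patient time, or how many events, will fall in each phase.

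**Step 3. Do the cross-references settle it?**

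- 5.7 refers to Section 6 for adverse event management.
- Section 6 returns high-dose steroid cases to 5.7, and its exceptions do not include pneumonitis.
- The start of Section 6 cites 5.6 for resuming treatment, but 5.6 covers removal from study; the resumption criteria are in 5.7.

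The references are circular, and no sentence gives one section precedence.

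**The case against.** The best defence is that the pneumonitis sentence in 5.7 restricts and does not grant permission: it warns of exacerbation and sets a stricter threshold than the general Grade 1 rule. It could be read as covering only patients in whom drug-associated pneumonitis has been excluded, or who turn out not to have needed steroids. Since 5.7 defers to Section 6, and Section 6 tells sites to follow event-specific guidance, a specific-over-general reading would let the table prevail.

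Part of this stands. The sentence is cautious, and a careful site might reach that reading. But the sentence does not limit itself in this way. It speaks of residual inflammation and sits among rules for steroid-treated immune events, while patients found not to have such an event have their own separate sentence in 5.7 and again in Section 6. The return of high-dose steroid cases to 5.7 also weakens the specific-over-general argument.

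Two wider conflicts might be inferred, and the documents support neither:

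- **A conflict at Grade 3 as well**, because the steroid clause also appears in that row. For steroid-treated patients 5.4, 5.7 and the table all stop drug.
- **The same conflict for pancreatitis**, because 5.7 lists it and Section 6 says "Patients who develop symptomatic pancreatitis or DM should be taken off treatment". That clause appears only in the Grade 3 and Grade 4 rows, where 5.7 also discontinues nivolumab after steroids. The Grade 2 row allows continuation if asymptomatic and has no off-treatment clause, so no conflict is shown for steroid-treated Grade 2 pancreatitis.

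**Conclusion.** The protocol contradicts itself for steroid-treated Grade 2 pneumonitis. The open case is clearest in Cohort B monotherapy from cycle 5; during induction the inconsistency lies within 5.7. The conclusion rests on reading the corticosteroid paragraphs of 5.7 as applying to immune pneumonitis, which is their plain sense.

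The point is narrow, and its frequency cannot be given. A reader might take an any-grade pneumonitis rate from within the at-most-20% band of the adverse event lists and calculate the chance of at least one case in 25 patients. That would count the wrong event: the conflict needs Grade 2 disease, steroids, full recovery and 2 weeks off steroids, and the documents give no rate for that combination.

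A reader might also infer that each case moves the response or PFS rate by 1/25 = 4 percentage points. That would hold only if the choice of rule changed the patient's endpoint status, which the documents do not establish. A response already confirmed stands, and 13.6.2 keeps eligible patients in the main response analysis. Nor do 5.5 and 5.6 say that going off study ends tumour assessment. The express promise in 5.5 to follow to progression covers only patients who complete therapy, so any gap there affects toxicity stops in general. The case for correction is consistent handling of re-exposure, and does not depend on a quantified effect on the endpoints.

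**What to change.** Reconcile four places so that steroid-treated Grade 2 pneumonitis has one outcome in both treatment phases: the combination paragraph of 5.7, the corticosteroid paragraphs of 5.7, the Grade 2 row of the Section 6 pneumonitis table, and the closing text of Section 6 that returns high-dose steroid cases to 5.7. State which section takes precedence where a general rule and an event table differ. If the retreatment sentence in 5.7 was meant only for patients in whom drug-associated pneumonitis has been excluded, it should say so. Correct the pointer at the start of Section 6 from 5.6 to the section that holds the resumption criteria. The clinical team decides which rule stands.

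The cost is a wording change in an amendment, with no additional patients, visits or data.

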5.8 Treatment of Nivolumab or Ipilimumab Related Infusion Reactions

Since nivolumab and ipilimumab contains only human immunoglobulin protein sequences, it is unlikely to be immunogenic and induce infusion or hypersensitivity reactions. However, if such a reaction were to occur, it might manifest with fever, chills, rigors, headache, rash, urticaria, angioedema, pruritis, arthralgias, hypo- or hypertension, bronchospasm, or other symptoms.

All Grade 3 or 4 infusion reactions should be reported as an SAE if criteria are met. Infusion reactions should be graded according to NCI CTCAE version 5.0 guidelines.

Treatment recommendations are provided below and may be modified based on local treatment standards and guidelines as medically appropriate:

For Grade 1 symptoms: (Mild reaction; infusion interruption not indicated; intervention not indicated)

Remain at bedside and monitor subject until recovery from symptoms. Infusion rate may be slowed. If the infusion is interrupted, then restart the infusion at 50% of the original infusion rate when symptoms resolve; if no further complications ensue after 30 minutes, the rate may be increased to 100% of the original infusion rate. Monitor patient closely.

The following prophylactic premedications are recommended for future infusions: diphenhydramine 50 mg (or equivalent) and/or paracetamol 325 to 1000 mg (acetaminophen) at least 30 minutes before additional nivolumab administrations, slowing infusion rate as above.

For Grade 2 symptoms: (Moderate reaction requires therapy or infusion interruption but responds promptly to symptomatic treatment [e.g., antihistamines, non-steroidal anti-inflammatory drugs, narcotics, corticosteroids, bronchodilators, IV fluids]; close observation for recurrence and treatment medications may need to be continued for 24-48 hours).

Stop the nivolumab infusion, begin an IV infusion of normal saline, and treat the subject with diphenhydramine 50 mg IV (or equivalent) and/or paracetamol 325 to 1000 mg (acetaminophen); remain at bedside and monitor patient until resolution of symptoms. Corticosteroid or bronchodilator therapy may also be administered as appropriate. If the infusion is interrupted, then restart the infusion at 50% of the original infusion rate when symptoms resolve; if no further complications ensue after 30 minutes, the rate may be increased to 100% of the original infusion rate. Monitor patient closely. If symptoms recur, then no further nivolumab will be administered at that visit. Administer diphenhydramine 50 mg IV, and remain at bedside and monitor the patient until resolution of symptoms. The amount of study drug infused must be recorded on the electronic case report form (eCRF). The following prophylactic premedications

are recommended for future infusions: diphenhydramine 50 mg (or equivalent) and (acetaminophen) (or paracetamol) 325 to 1000 mg should be administered at least 30 minutes before additional nivolumab administrations. If necessary, corticosteroids (recommended dose: up to 25 mg of IV hydrocortisone or equivalent) may be used.

For Grade 3 or Grade 4 symptoms: (Severe reaction), Grade 3 symptoms: prolonged [*i.e.*, not rapidly responsive to symptomatic medication and/or brief interruption of infusion]; recurrence of symptoms following initial improvement; hospitalization indicated for other clinical sequelae [*e.g.*, renal impairment, pulmonary infiltrates]).

Grade 4 symptoms: (life threatening; pressor or ventilatory support indicated).

Immediately discontinue infusion of nivolumab. Begin an IV infusion of normal saline, and treat the subject as follows. Recommend bronchodilators, epinephrine 0.2 to 1 mg of a 1:1,000 solution for subcutaneous administration or 0.1 to 0.25 mg of a 1:10,000 solution injected slowly for IV administration, and/or diphenhydramine 50 mg IV with methylprednisolone 100 mg IV (or equivalent), as needed. Patient should be monitored until the investigator is comfortable that the symptoms will not recur. Nivolumab will be permanently discontinued. Investigators should follow their institutional guidelines for the treatment of anaphylaxis. Remain at bedside and monitor patient until recovery from symptoms. In the case of late-occurring hypersensitivity symptoms (*e.g.*, appearance of a localized or generalized pruritis within 1 week after treatment), symptomatic treatment may be given (*e.g.*, oral antihistamine, or corticosteroids).

Please note that late occurring events including isolated fever and fatigue may represent the presentation of systemic inflammation. Please evaluate accordingly.

5.9 Treatment Beyond Progression

A minority of subjects treated with immunotherapy may derive clinical benefit either delayed responses, stable disease, or increased overall survival despite initial evidence of progressive disease (PD) with nivolumab or combination treatment.

Patients may be permitted to continue treatment beyond initial RECIST 1.1-defined PD that occurs during the initial (24 weeks) of treatment as long as they meet the following criteria:

- No more than 4 new lesions total sum of the longest diameter (SHORT diameter for LN) cannot exceed 40% of the initial sum including new lesions
- Patients must be clinically stable with no change in performance status due to disease progression
- No indication for immediate alternative treatment
- Patient [assessed by the investigator] is showing clinical benefit and tolerates study drug. The assessment of clinical benefit should take into account whether the subject is clinically stable or deteriorating and likely or unlikely to receive further benefit from continued treatment.

- The time of progression is noted from the first assessment that exceeds standard criteria

New lesions are considered measurable at the time of initial progression if the longest diameter is at least 10 mm (except for pathological lymph nodes, which must have a short axis of at least 15 mm). Any new lesion considered non-measurable at the time of initial progression may become measurable and therefore included in the tumor burden measurement if the longest diameter increases to at least 10 mm (except for pathological lymph nodes, which must have an increase in short axis to at least 15 mm).

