11 MEASUREMENT OF EFFECT

11.1 Antitumor Effect – Solid Tumors

For the purposes of this study, patients should be re-evaluated for response every 8 weeks (+/- 2 days). In addition to a baseline scan, confirmatory scans should also be obtained at least 4 weeks following initial documentation of objective response.

Response and progression will be evaluated in this study using the new international criteria proposed by the revised Response Evaluation Criteria in Solid Tumors (RECIST) guideline (version 1.1) [Eur J Ca 45:228-247, 2009]. Changes in the largest diameter (unidimensional measurement) of the tumor lesions and the shortest diameter in the case of malignant lymph nodes are used in the RECIST criteria.

All patients who receive at least one dose of nivolumab and ipilimumab each will be included in the toxicity analysis. This includes participants who receive study drug and are ultimately deemed ineligible.

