Target lesions. All measurable lesions up to a maximum of 2 lesions per organ and 5 lesions in total, representative of all involved organs, should be identified as **target lesions** and recorded and measured at baseline. Target lesions should be selected on the basis of their size (lesions with the longest diameter), be representative of all involved organs, but in addition should be those that lend themselves to reproducible repeated measurements. It may be the case that, on occasion, the largest lesion does not lend itself to reproducible measurement in which circumstance the next largest lesion which can be measured reproducibly should be selected. A sum of the diameters (longest for non-nodal lesions, short axis for nodal lesions) for all target lesions will be calculated and reported as the baseline sum diameters. If lymph nodes are to be included in the sum, then only the short axis is added into the sum. The baseline sum diameters will be used as reference to further characterize any objective tumor regression in the measurable dimension of the disease.

Non-target lesions. All other lesions (or sites of disease) including any measurable lesions over and above the 5 target lesions should be identified as **non-target lesions** and should also be recorded at baseline. Measurements of these lesions are not required, but the presence, absence, or in rare cases unequivocal progression of each should be noted throughout follow-up.

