11.1.4.1 Evaluation of Target Lesions

Complete Response (CR): Disappearance of all target lesions. Any pathological lymph nodes (whether target or non-target) must have reduction in short axis to <10 mm (<1 cm).

Partial Response (PR): At least a 30% decrease in the sum of the diameters of target lesions, taking as reference the baseline sum diameters.

Progressive Disease (PD): At least a 20% increase in the sum of the diameters of target lesions, taking as reference the smallest sum on study (this includes the baseline sum if that is the smallest on study). In addition to the relative increase of 20%, the sum must also demonstrate an absolute increase of at least 5 mm (0.5 cm). (Note: the appearance of one or more new lesions is also considered progressions).

Stable Disease (SD): Neither sufficient shrinkage to qualify for PR nor sufficient increase to qualify for PD, taking as reference the smallest sum diameters while on study.

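### The 40% size limit for treatment beyond progression (5.9) is defective as written: taken literally it bars all progressors without deep prior shrinkage, and its two workable readings disagree

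*Combined protocol and SAP*

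**What the plan says.** All references are to the combined protocol and SAP.

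- **5.9, purpose.** A minority of patients "may derive clinical benefit either delayed responses, stable disease, or increased overall survival despite initial evidence of progressive disease".
- **5.9, scope.** Continuation may be permitted after "PD that occurs during the initial (24 weeks) of treatment", and only "as long as they meet the following criteria".
- **5.9, first criterion.** One unpunctuated bullet sets a maximum of four new lesions and then states "total sum of the longest diameter (SHORT diameter for LN) cannot exceed 40% of the initial sum including new lesions". No other section restates or explains the 40%.
- **5.9, last paragraph.** New lesions of at least 10 mm (15 mm short axis for nodes) are measurable. A new lesion that is too small at first "may become measurable and therefore included in the tumor burden measurement".
- **11.1 and 11.1.2.** For timing, "patients should be re-evaluated for response every 8 weeks". The sum over target lesions "will be calculated and reported as the baseline sum diameters".
- **11.1.4.1.** Target-lesion progression (PD) is a rise of at least 20% and at least 5 mm from the smallest sum on study; "this includes the baseline sum if that is the smallest on study". Partial response (PR) is a fall of at least 30% from baseline.
- **5.4 and 5.6.** Both send stopping and removal for progression to 5.9.
- **13.1, Cohort B.** Patients treated beyond progression may be designated delayed responders and counted in the two-stage rule: at least 1 of 8 to proceed, at least 3 of 25 to accept.

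**The concern.** The criterion applies only to patients whose disease has already progressed, yet its words require a total burden of at most 40% of the starting sum. For a patient who progresses by growth without earlier shrinkage, the two conditions cannot both hold. If the limit was meant as a permitted rise, the word *increase* is missing. If it was meant for new lesions alone, the wording does not say so clearly.

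The bullet is operative. It helps decide who stops treatment and who remains under observation long enough to become a delayed responder. Beyond the off-study assessment, 5.5 and note c of the Cohort B calendar provide for continued tumor measurement only in patients who complete all planned therapy. A response after stopping for progression could therefore go unseen. With thresholds of 1 and 3 responders, one patient handled differently could matter, and sites that read the bullet differently would ascertain response differently.

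**Working it through.** The 40% is stipulated, so there is no planned figure to reproduce. The check is whether a patient can have PD and also meet the limit.

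**Inputs.** B = baseline sum; N = smallest sum on study; T = current target sum; L = summed measurable new lesions. The PD, PR and 10 mm rules are as given above. B = 100 mm and the other baselines are illustrative assumptions.

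**1. Literal limit, first scan (week 8).** The smallest sum is the baseline, so N = B. Target-growth PD means T ≥ 1.20B; the limit is 0.40B. Since 1.20 / 0.40 = 3, no target-growth progressor qualifies.

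**2. Literal limit, later scans.** PD needs T ≥ max(1.20N, N + 5). Requiring T ≤ 0.40B as well gives N ≤ min(B/3, 0.40B − 5).

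- B = 100: min(33.3, 35) = 33.3 mm, a 66.7% fall before progression.
- B = 75: min(25, 25) = 25 mm, 66.7%. The two bounds meet here.
- B = 50: min(16.7, 15) = 15 mm, 70%.
- B = 20: min(6.7, 3) = 3 mm, 85%.

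Scans every 8 weeks put at most 24 / 8 = 3 scheduled assessments inside the 24-week window, so that fall and the regrowth would both have to be seen within it.

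**3. Literal limit, PD by a new lesion.** With one 10 mm lesion, T ≤ 0.40B − 10.

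- B = 100: T ≤ 30 mm, a 70% fall.
- B = 50: T ≤ 10 mm, an 80% fall.
- With no measurable new lesion (L = 0): T ≤ 0.40B, a 60% fall.

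All of these are deeper than the 30% fall that defines PR.

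**4. The three readings compared, B = 100 mm.** Literal: T + L ≤ 40. Total increase of at most 40%: T + L ≤ 140. New lesions only: L ≤ 40. Each row assumes at most four new lesions and that the other criteria are met.

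| Case | Literal | Total increase | New lesions only |
|---|---|---|---|
| T 120, no new lesion (week 8) | no | yes | yes |
| T 100 + L 10 (total 110) | no | yes | yes |
| N 35, then T 42 | no | yes | yes |
| N 30, then T 37 | yes | yes | yes |
| T 28 + L 10 (total 38) | yes | yes | yes |
| T 70 + L 45 (total 115) | no | yes | no |
| T 125 + L 20 (total 145) | no | no | yes |
| T 150, no new lesion | no | no | yes |

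The last three rows separate the two workable readings.

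**5. Design figures.** The exact two-stage binomial for Cohort B (8 then 25 patients, at least 1 then at least 3 responses) gives type I error 0.094 at 5%, power 0.938 at 30%, and early stopping 0.95^8 = 0.663. The plan states 9%, 94% and 66%. None of these uses the 5.9 limit.

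**The case against.** The best defense is that this is a drafting slip no sensible investigator would follow. The section title, its opening sentence and a remark in 5.7 about benefit after progression all point away from a 60% shrinkage requirement. The list is loose elsewhere too: its last item is a rule for dating progression, not a criterion. Continuation is permissive and also depends on clinical stability, no need for other treatment and investigator-assessed benefit.

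A second defense is that no word need be missing. Run together, the bullet can mean at most four new lesions whose combined size is at most 40% of the initial sum, and then the section works.

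Much of this stands. Nothing shows that any site applied the literal text, and the new-lesions-only reading cannot be excluded. But the second defense does not remove the problem, because the two workable readings decide some patients in opposite ways. The total-increase reading fits better: the text speaks of a total sum that includes new lesions, and the last paragraph of 5.9 adds measurable new lesions to the tumor burden. That remains an inference.

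Two stronger readings are tempting. One is that the documents establish a 140% limit with a word dropped; they never state it. The other is that, under the literal text, a target-growth progressor who qualifies could only re-confirm an earlier response, so that only new-lesion or non-target progressors could add one. That fails because 11.1.4.3 requires confirmation at 4 weeks or more. An earlier PR that was never confirmed would not have counted, so a later delayed response could still add a responder.

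**Conclusion.** The point holds: the first continuation criterion is wrong as written and should be corrected. Literally, it excludes every target-growth progressor at the first scan, and every later one whose target sum had not fallen to one third of baseline or less (lower still when the baseline sum is under 75 mm). It is not strictly impossible to meet, since deep responders who then progress can pass. Its two workable readings conflict in identifiable cases.

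The size is modest. Cohort A is closed, so the prospective reach is Cohort B, at most 25 patients. The number affected and any change in the response count cannot be found from the documents. Stated power, type I error and stopping probability do not change, and progression is still dated at the initial event. The conclusion rests on the PD rule in 11.1.4.1 and on taking the initial sum to be the baseline sum of 11.1.2, which the sponsor should confirm.

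**What to change.** Split the bullet into two criteria:

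- (a) At most four new lesions have appeared.
- (b) Target lesions plus measurable new lesions (longest diameter, or short axis for lymph nodes) sum to at most 140% of the baseline sum, that is, a rise of no more than 40%.

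The sponsor should confirm that (b) is the intent and that baseline, not the smallest sum on study, is the reference. If new lesions alone were meant, (b) should say so and state whether target growth is limited.

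The cost is a one-bullet protocol clarification. Sample size, decision rules, visits and stated error rates stay as they are.
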